APPENDIX VII: SCHEDULE OF PROCEDURES

- Imaging Scans: Prior to the first Therapeutic Dose of Ultratrace iobenguane I 131, subjects will be given an Imaging Dose of Ultratrace iobenguane I 131, followed by three scans. Within seven days after each Therapeutic Dose of Ultratrace iobenguane I 131 subjects will have an additional Ultratrace iobenguane I 131 scan to further assess biodistribution. 12
- EORTC QLQ-C30 and NIH Pheo/Paraganglioma Questionnaire will be administered at Screening/Baseline (twice) before the first therapeutic dose, Week 3, Week 6, Week 10, Week 12, Week 18, Week 22, and monthly from 6-12 months following the first Therapeutic Dose. 13

Ultratrace Iobenguane I 131 Protocol No. MIP-IB12B

1. LIST OF ABBREVIATIONS

AE	Adverse Event/Experience
AESI	Adverse Events of Special Interest
ALT/SGPT	Alanine Aminotransferase
ANC	Absolute Neutrophil Count
AST/SGOT	Aspartate Aminotransferase
bpm	Beats per Minute
BSA	Body Surface Area
C	Celsius
CR	Complete Response
CRF	Case Report Form
CSR	Clinical Study Report
CT	Computed Tomography
CTCAE	Common Terminology Criteria for Adverse Events
ECG	Electrocardiogram
EORTC	European Organisation for Research and Treatment of Cancer
F	Fahrenheit
FDG	Fluorodeoxyglucose
h	Height
Hg	Mercury
HGB	Hemoglobin
I	Iodine
ICH	International Conference on Harmonisation of Technical Requirements for Pharmaceuticals for Human Use
kg	Kilogram
LLN	Lower Limit of Normal
ln	Natural Logarithm
mCi	Millicurie
MedDRA	Medical Dictionary for Regulatory Activities
MIBG	Metaiodobenzylguanidine
MIP	Molecular Insight Pharmaceuticals, Inc.
mL	Milliliter
mm	Millimeter
MR	Magnetic Resonance or Moderate Response (per context)
MRI	Magnetic Resonance Imaging
msec	Millisecond
N	Sample Size
NE	Not Evaluable
ng	Nanogram
NIH	National Institutes of Health
PD	Progressive Disease
PR	Partial Response
QoL	Quality of Life
RECIST	Response Evaluation Criteria in Solid Tumors

SAE	Serious Adverse Event
SAP	Statistical Analysis Plan
SD	Standard Deviation or Stable Disease (per context)
SLD	Sum of Longest Diameters
SOP	Standard Operating Procedure
SSKI	Potassium Iodide
TEAE	Treatment-Emergent Adverse Event
ULN	Upper Limit of Normal
w	Weight
WBC	White Blood Cells
WHO	World Health Organization

2. INTRODUCTION

This study is designed to study the efficacy of AZEDRA[®] iobenguane I 131 (or iobenguane I 131) for the treatment of relapsed/refractory malignant pheochromocytoma and paraganglioma. The purpose of this statistical analysis plan (SAP) is to specify how the data collected in this trial will be summarized and analyzed. The descriptive summaries and inferential analyses described in this SAP will provide the foundation for drawing conclusions about the outcome of the study. This SAP follows the principles set forth in E9 Statistical Principles for Clinical Trials.^[1]

3. SCOPE

This SAP specifies the analyses that are planned prospectively for data collected in the study clinical database and provided in clinical datasets by Data Management at Molecular Insight Pharmaceuticals Inc., a wholly-owned subsidiary of Progenics Pharmaceuticals, Inc. This includes data captured on the Case Report Form (CRF), data from the clinical safety database, clinical laboratory and electrocardiogram (ECG) data provided by central labs, and image evaluation data provided by the central reviewer.

Radiation dose estimates to some normal organs (i.e., results of the pre-treatment dosimetry study) are not captured in the clinical database. Analysis of these data is the subject of a separate report.

Additional analyses of study data not pre-specified in this SAP may be performed on an ad hoc basis. If the decision is made to include additional analyses, the details will be provided in a SAP addendum prior to their conduct.

4. STUDY OBJECTIVES AND ENDPOINTS

4.1. Overview of Study

This is a multi-center, open-label, single arm study. This study was initiated in June 2009 and patient enrollment was completed in December 2015. Fifty-eight subjects were planned to be given two Therapeutic Doses each at 500 mCi (or 8 mCi/kg for subjects weighing 62.5 kg or less) of iobenguane I 131. Prior to administration of the first Therapeutic Dose, subjects will be given an Imaging Dose (3 mCi – 6 mCi) of iobenguane I 131 and will undergo iobenguane I 131 scintigraphic scans to evaluate tumor avidity as well as to measure normal organ distribution and allow for the calculation of radiation dosimetry to normal organs. The Therapeutic Dose for a subject will be appropriately decreased if results of the dosimetry study indicate an adjustment is warranted.

Tumors will be measured by computed tomography (CT) or magnetic resonance (MR) at baseline and at 3, 6, 9 and 12 months after the first Therapeutic Dose. A bone scan will be performed at baseline, and if bone lesions are found or suspected, additional bone scans will be performed as appropriate. Overall tumor response at 3, 6, 9 and 12 months per RECIST criteria will be assessed centrally by independent, blinded readers. To assess viable tumor tissue, fluorodeoxyglucose (FDG) scans may be performed (optional, if available at study site). Tumor markers (such as serum chromogranin A [CgA]) will be evaluated by a central laboratory at intervals described in the protocol. Use and dose of antihypertensive, pain and other medication required for tumor associated signs and symptoms will be recorded on an on-going basis. Subject-reported Quality of Life (QoL) measurements will be obtained through the EORTC QLQ-C30 v3 and the NIH Quality of Life and Symptoms Questionnaire for Pheochromocytoma and Paraganglioma. The frequency of the procedures is summarized in the Schedule of Procedures in the Study Protocol. Subjects may undergo additional assessments as warranted (for example, to confirm tumor response) at unscheduled visits.

Safety will be assessed through analyses of treatment emergent adverse events (TEAEs), as well as baseline and pre- and post-infusion ECGs, physical examinations, vital signs measurements, and laboratory measurements (including clinical chemistry, hematology and urinalysis). Serious adverse events (SAEs) and non-SAEs will be collected and reported until 16 weeks following the last administration of iobenguane I 131. Adverse events of special interest (AESIs), including radiation toxicity, reported beyond 16 weeks after the last therapeutic dose of study drug will be collected during the 12 month assessment period and until completion of the follow up period.

After the 12-month assessment, subjects enter long-term follow-up and remain in follow-up for a total of 5 years following the first therapeutic dose. Subjects will be followed for AESIs and overall survival for 5 years post-treatment. In years 2-5 post-treatment (or until a subject experiences disease progression, start of another anticancer therapy or death), data on tumor response, tumor markers and clinical benefit (to month 18 only) will be collected through assessments provided by institutional standard of care.

4.2. Trial Objectives: Primary

The primary objective of this trial is to determine the proportion of study subjects with a reduction (including discontinuation) of all antihypertensive medication by at least 50% for at least six months or two cycles, from up to two Therapeutic Doses each at 500 mCi (or 8 mCi/kg, for subjects weighing

62.5 kg or less) of iobenguane I 131 administered approximately three months apart. A cycle is considered a three-month dosing interval.

4.3. Trial Objectives: Secondary

The secondary objectives of this trial are as follows:

- To evaluate the safety of iobenguane I 131 in subjects with malignant pheochromocytoma/paraganglioma, including human radiation absorbed dose estimates to normal organs.
- To assess the proportion of subjects with overall tumor response of CR or PR per RECIST criteria.
- To assess the proportion of subjects with overall tumor response of CR, PR or MR (moderate response, i.e., decrease in the sum of the longest diameters of the target lesions of 15-30%, with no evidence of progressive disease [PD] in non-target lesions) per RECIST criteria.
- To assess status of bone lesions using the Soloway Scale.
- To assess tumor marker response in 24 hr urine and other serum tumor markers associated with pheochromocytoma/paraganglioma.
- To describe changes from baseline in the overall QoL through the EORTC QLQ-C30 questionnaire post-treatment.
- To describe changes from baseline in symptoms using the NIH Quality of Life and Symptoms Questionnaire for Pheochromocytoma and Paraganglioma post-treatment.
- To assess change in use of analgesics and pain medications.
- To describe Karnofsky Performance Status post-treatment.
- To assess overall survival, up to 5 years post-treatment.

5. ANALYSIS SETS

Figure 1 is a flow diagram of the protocol-defined analysis sets.

5.2. Dosimetry Set/Safety Set

The Dosimetry Set/Safety Set includes all subjects who received the Imaging Dose.

[figure not shown]
5.3. Full Analysis Set

The Full Analysis Set is a subset of the Dosimetry Set/Safety Set, excluding subjects who did not receive at least the first Therapeutic Dose.

5.4. Per Protocol Set

The Per Protocol Set includes a subset of the Full Analysis Set, excluding subjects who received only one Therapeutic Dose, who did not attend the Month 3 and Month 6 efficacy visits, or with major protocol violations. Major protocol violations are defined as those that could impact the efficacy evaluation such as a subject is ineligible, missing key endpoint data, received an unauthorized treatment, etc. A review of the protocol deviations will be performed prior to database lock and the listing of all major violations will be identified and included as an addendum to the Analysis Plan.

Figure 1: Schematic of Protocol-Defined Analysis Sets

* Adverse Events prior to the Imaging Dose will be captured for all enrolled subjects and reported separately from treatment-emergent AEs.

6. DETERMINATION OF SAMPLE SIZE

The planned sample size for this study is 58 subjects, for which it is estimated that approximately 75 subjects may be enrolled. The one-sided alternative hypothesis of the study is that the proportion of subjects experiencing a reduction (including discontinuation) of all antihypertensive medications by at least 50% for at least six months or two cycles is 0.25, against the null hypothesis that the proportion is 0.10. Sample size was based on a one-sided significance level of $\alpha = 0.025$ and power of 0.90 (90%).

7. STATISTICAL METHODS

Standard descriptive statistics will be presented for data collected. For continuous measures, the mean, standard deviation (SD), median, range and sample size (N) will be presented; for categorical measures, frequency distributions including the number of subjects and percentages in each category will be presented. Correlations between outcomes will be computed and presented as appropriate (e.g., between levels of different tumor markers). Time-to-event data will be summarized using Kaplan-Meier methodology using 25th, 50th (median), and 75th percentiles with associated two-sided 95% confidence intervals, as well as percentage of censored observations.

Numbering for tables and listings will follow the following convention: tables will be numbered 14.x.x.x and listings will be numbered 16.2.x.x.x.

Additional descriptive or inferential analyses not described in this document will be performed on an ad hoc basis.

For the purpose of calculation of the primary endpoint and tumor marker reporting, a month is defined as 28 days to be consistent with the visit schedule. For the purposes of defining the 12-month efficacy period in which the primary endpoint benefit could begin, this period is 12 calendar months. For the calculation of overall survival using Kaplan-Meier methods, a month will be defined as a calendar month or 30.25 days to approximate calendar time.

For each study variable of interest, the subsections that follow provide: when and how it is to be measured; whether it will be summarized in a table, included in listings or displayed in figures; what additional statistical analyses, if any, will be performed using the variable.

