7. INTRODUCTION

7.1 Malignant Pheochromocytoma/Paraganglioma

Pheochromocytomas are rare tumors that arise from cells of the sympathetic nervous system and may secrete catecholamines. Such tumors are usually found within one or both adrenal glands (85%), but may arise in other areas of sympathetic nerve cells, and are then referred to as paragangliomas.²¹ About 15% are found to be malignant at the time, or immediately after, the primary tumor is discovered.¹⁷ Another 5% of individuals with pheochromocytomas are later found to have malignant or recurrent disease.

Common sites of metastatic disease include lung, lymph nodes, and bone. Although the effects of excessive catecholamine can be reduced by adrenergic blockade or blocking of catecholamine synthesis, these drugs do not halt tumor growth. Five-year survival has been 40%.¹ For malignant pheochromocytoma; radiation therapy has been palliative but not curative. Chemotherapy trials have failed to produce cures or significant remissions. A study of the CVD regimen (cyclophosphamide + vincristine + dacarbazine) in 14 patients with malignant pheochromocytoma reported a complete or partial response in 57% of patients (median duration, 21 months) in this very small patient study; importantly, disease progression occurred in 9 of the 14 patients and there were 6 deaths with short term follow-up.² Patients recently diagnosed with malignant pheochromocytoma have tumors that initially can be slow growing even though the survival rate is less than 50%; although some patients may experience minimal morbidity with survival for as long as 20 years.³ Rather than newly diagnosed non-metastatic malignant pheochromocytoma, this study will focus on patients with metastatic malignant pheochromocytoma or paraganglioma who have failed other therapies or are not candidates for chemotherapy or other curative therapies.

In this setting of more rapidly growing and progressive lesions, survival is often 24 months or less.

7.2 Carrier-Added Iobenguane I 131

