7.4.9. Tumor Pain Medicine

Pain medication used to relieve tumor pain will be defined as medication identified in the case report form to relieve tumor pain.

A shift table for tumor pain medication usage by subject will be presented by visit, with pain medication usage categorized into three intensity levels: any opioid use, other pain medication use, and no pain medication use. This categorization will be made based on usage at 3 months (91 days), 6 months (182 days), 9 months (273 days), and 12 months (365 days) post first therapeutic dose. Analgesics identified for other uses will not be included in this summary.

A separate listing of analgesic medications other than those used for tumor pain reduction will be provided.

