7.4.11. Overall Survival

Overall survival (OS) is defined as the time from the date of first therapeutic dose to the date of death from any cause. OS time will be censored at the last date the subject is known to be alive. The Kaplan-Meier predicted survival rates at Years 1-5 will be reported. Overall survival will be listed and Kaplan-Meier curves will be prepared. The last date that the patient was confirmed to be alive will be obtained from information reported by the clinical site: if this information is collected outside of the CRF the last date the subject is known to be alive or date of death reported from the site will be provided in a spreadsheet and integrated into analysis datasets.

Overall survival will also be presented by primary endpoint status.

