APPENDIX 1. VISIT WINDOWS

These windows are intended for data summaries by time point. When multiple assessments fall within a window, the assessment closest to the nominal time will be used in summaries. If there are multiple visits equally distant from the midpoint of a window, then the earlier visit will be used.

Efficacy Assessments

No	End Point	From Imaging Dose 1	From Therapeutic Dose 1	From Therapeutic Dose 2
1	Overall Tumor Response (CT/MRI Scans)	Screening / Baseline (Day -28 to Day 0)	Month 3 (Day 81 - Day 101) Month 6 (Day 173 - Day 193) Month 9 (Day 264 - Day 284) Month 12 (Day 355 - Day 375) Month 18 (Day 518 - Day 578) Month 24 (Day 700 - Day 760) Month 30 (Day 883 - Day 943) Month 36 (Day 1065 - Day 1125) Month 42 (Day 1248 - Day 1308) Month 48 (Day 1430 - Day 1490) Month 54 (Day 1613 - Day 1673) Month 60 (Day 1795 - Day 1855)	
2	Tumor Markers	Screening / Baseline (Day -28 to Day 0)	Week 2 (Day 8 - Day 14) Week 4 (Day 22 - Day 28) Week 6 (Day 36 - Day 42) Week 8 (Day 50 - Day 56) Week 10 (Day 64 - Day 70) Week 12 (Day 78 - Day 84) Week 14 (Day 92 - Day 98) Week 16 (Day 106 - Day 112) Week 18 (Day 120 - Day 126) Week 20 (Day 134 - Day 140) Week 22 (Day 148 - Day 154) Week 24 (Day 162 - Day 168) Month 7 (Day 203 - Day 223)	

No	End Point	From Imaging Dose 1	From Therapeutic Dose 1	From Therapeutic Dose 2
			Month 8 (Day 233 - Day 253) Month 9 (Day 264 - Day 284) Month 10 (Day 294 - Day 314) Month 11 (Day 325 - Day 345) Month 12 (Day 355 - Day 375) Month 18 (Day 518 - Day 578) Month 24 (Day 700 - Day 760) Month 30 (Day 883 - Day 943) Month 36 (Day 1065 - Day 1125) Month 42 (Day 1248 - Day 1308) Month 48 (Day 1430 - Day 1490) Month 54 (Day 1613 - Day 1673) Month 60 (Day 1795 - Day 1855)	
3	Soloway Score (Bone Scan) and optional FDG-PET Scan	Screening / Baseline (Day -28 to Day 0)	Month 3 (Day 81 - Day 101) Month 6 (Day 173 - Day 193) Month 9 (Day 264 - Day 284) Month 12 (Day 355 - Day 375)	
4	Karnofsky Performance	Screening / Baseline (Day -28 to Day 0)	Day 1 Week 6 ± 10 days (Day 32 - Day 52) Month 3 (Day 81 - Day 101) Month 6 (Day 173 - Day 193) Month 9 (Day 264 - Day 284) Month 12 (Day 355 - Day 375)	Day 1 Week 6 ± 10 days (Day 32 - Day 52)

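### The 30.25-day month in the SAP's overall survival definition implies a 363-day year, and the same sentence also permits a true calendar month; the numerical effect is small and depends on how the rule is programmed

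*SAP*

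**What the plan says.** SAP section 7 (Statistical Methods) gives different month lengths for different purposes. For the primary endpoint and tumor marker reporting, "a month is defined as 28 days to be consistent with the visit schedule". The 12-month efficacy period is measured in calendar months. Survival has its own rule, introduced by "For the calculation of overall survival using Kaplan-Meier methods": "a month will be defined as a calendar month or 30.25 days to approximate calendar time". The same section summarizes time-to-event data by the 25th, 50th and 75th percentiles with 95% confidence intervals.

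SAP section 7.4.11 fixes the origin and the event: "Overall survival (OS) is defined as the time from the date of first therapeutic dose to the date of death from any cause". It adds: "The Kaplan-Meier predicted survival rates at Years 1-5 will be reported". It gives no day count for a year and does not say how the yearly marks are located on the curve.

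Two other places show the year length that the SAP uses. Section 7.4.9 classifies pain medication at "12 months (365 days) post first therapeutic dose". Appendix 1 ends its tumor response and tumor marker windows with "Month 60 (Day 1795 - Day 1855", whose midpoint is Day 1825, or 5 x 365.

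**The concern.** The sentence states its own aim, to track calendar time, and 30.25 is the only number it offers. That number is too small for the aim. A programmer who needs a divisor will probably use it, and dividing days by too short a month makes every survival time in months too long. If the yearly marks are built from the same month, each falls before the true anniversary. A Kaplan-Meier curve never rises, so any resulting change in a yearly rate would be in the favorable direction.

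The wording also leaves a choice. Two programmers could both follow the SAP, one counting calendar months and one dividing by 30.25, and print different survival times for the same subject. What is at stake is the accuracy and reproducibility of a descriptive secondary endpoint.

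**Working it through.** **Inputs.** Month length 30.25 days (SAP section 7). Rates at Years 1 to 5 (SAP 7.4.11). Twelve months as 365 days (SAP 7.4.9). Window midpoints for Months 12, 24, 36, 48 and 60 at Days 365, 730, 1095, 1460 and 1825 (SAP Appendix 1). Only to size the effect, three 5-year survival figures from the protocol: 40% (section 7.1), and 64% and 85% (two carrier-added series in section 7.2).

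**1. Can 30.25 be reproduced?** Average month = days per year / 12.

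- 364/12 = 30.333
- 365/12 = 30.417
- 365.2425/12 = 30.437
- 365.25/12 = 30.4375
- 366/12 = 30.5

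None gives 30.25. It requires a year of 12 x 30.25 = 363 days.

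**2. Effect on months, if 30.25 is the divisor.** 30.4375/30.25 = 1.0062, an overstatement of 0.62% (0.55% against a 365-day year). A true 24 months prints as 24.15, 36 as 36.22 and 60 as 60.37.

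**3. Effect on the yearly marks, if Year y is also read at 12y such months.**

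| Year | Day at 12y x 30.25 | Day at 365.25y | Days early | Days early against 365y |
|---|---|---|---|---|
| 1 | 363 | 365.25 | 2.25 | 2 |
| 2 | 726 | 730.5 | 4.5 | 4 |
| 3 | 1089 | 1095.75 | 6.75 | 6 |
| 4 | 1452 | 1461 | 9.0 | 8 |
| 5 | 1815 | 1826.25 | 11.25 | 10 |

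**4. Expected effect on a survival rate.** Assume a constant hazard. With S the true 5-year survival, the value read at Year 5 is S^(1815/1826.25).

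- S = 0.40: reads 0.4023, excess 0.23 percentage points
- S = 0.64: reads 0.6418, excess 0.18 points
- S = 0.85: reads 0.8509, excess 0.09 points

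At Year 1 the excesses are 0.09, 0.05 and 0.02 points.

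**5. Chance that the Year 5 rate changes at all.** It changes only if a death falls in the 11.25-day gap. The number treated is not in the documents, so assume N = 58 to 75 (the planned evaluable and enrolled numbers) and no censoring. Expected deaths in the gap are about N x S x (-ln S) x 11.25/1826.25, and the chance of none is exp(-expected).

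- S = 0.40: 0.13 to 0.17 expected, so 84% to 88% chance of none
- S = 0.64: 0.10 to 0.13 expected, so 88% to 90% chance of none
- S = 0.85: 0.05 to 0.06 expected, so 94% to 95% chance of none

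If one death did fall there, the excess would be 1/75 = 1.3 to 1/58 = 1.7 points. The averages in step 4 are therefore mostly zero with an occasional larger step.

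**The case against.** The strongest reply is that the SAP never commits to the faulty calculation. Its sentence names the calendar month first, and true calendar months introduce no error. Section 7.4.11 states its time points in years, and a reading by date or at multiples of 365.25 days would give no shift. A reader might infer that every survival quantile will be inflated and that the yearly rates will be read 2 to 11 days early. The documents do not support that as a flat statement. The inflation needs 30.25 as the divisor, and the early reading also needs years built as multiples of twelve such months. This part of the objection stands.

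A reader might also see a contradiction between 30.25 and the Appendix 1 windows. That is too strong. Overall survival is not among the endpoints listed there, and section 7 deliberately uses different months for different purposes, including a 28-day month that is not in question. The windows show which year length the SAP uses on a calendar scale, but they do not govern survival. The firm inconsistency is between 30.25 and the aim stated in its own sentence.

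Finally, no decision depends on it. Overall survival has no hypothesis test or benchmark, and trial success rests on the antihypertensive endpoint alone. Survival by primary endpoint status uses the same scale in both groups. This also stands, and it limits the importance of the point. None of it makes 30.25 a correct approximation or removes the choice of two rules.

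**Conclusion.** The point holds as a minor error in an analysis constant, together with an ambiguous definition. That 30.25 days does not approximate a calendar month follows from arithmetic alone and needs no assumption. That the sentence allows two different results for one subject follows from its wording.

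The consequences are conditional. Using 30.25 as the divisor lengthens survival in months by 0.62%. Reading Years 1-5 at multiples of twelve such months as well moves the marks 2.25 to 11.25 days early, which can leave a rate unchanged or raise it but never lower it. The expected excess at Year 5 is 0.09 to 0.23 percentage points, given a constant hazard and 5-year survival between 85% and 40%. With 58 to 75 treated subjects and no censoring, the chance that the Year 5 rate changes at all is roughly 5% to 16%.

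The order of events, the shape of the curve, the proportion censored, the primary endpoint and the sample size are untouched.

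**What to change.** In SAP section 7, replace the survival clause with a single rule: a month is 30.4375 days (365.25/12). Delete the calendar-month alternative. In section 7.4.11, add that the Year 1-5 Kaplan-Meier rates are read at 365.25, 730.5, 1095.75, 1461 and 1826.25 days from the first therapeutic dose. Enter the change in the table in SAP section 9.

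The cost is one clause, one added sentence and one constant in the program. The only downside is that reported months may be about 0.6% shorter than under the 30.25-day divisor.
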